Potentially leading to amputation	10053692	Wound complication
Potentially leading to amputation	10053716	Wound necrosis
Potentially leading to amputation	10054044	Diabetic microangiopathy
Potentially leading to amputation	10056340	Diabetic ulcer
Potentially leading to amputation	10056418	Arterial bypass operation
Potentially leading to amputation	10056673	Peripheral sensorimotor neuropathy
Potentially leading to amputation	10057518	Peripheral artery angioplasty
Potentially leading to amputation	10057525	Peripheral artery occlusion
Potentially leading to amputation	10058041	Wound sepsis
Potentially leading to amputation	10058042	Wound abscess
Potentially leading to amputation	10059245	Angiopathy
Potentially leading to amputation	10059385	Extremity necrosis
Potentially leading to amputation	10059442	Wound infection staphylococcal
Potentially leading to amputation	10059444	Wound infection pseudomonas
Potentially leading to amputation	10060734	Diabetic foot
Potentially leading to amputation	10060803	Diabetic foot infection
Potentially leading to amputation	10060963	Arterial disorder
Potentially leading to amputation	10060965	Arterial stenosis
Potentially leading to amputation	10061627	Amputation
Potentially leading to amputation	10061655	Arterial graft
Potentially leading to amputation	10061657	Arterial stent insertion

Statistical Analysis Plan

Version: 3

Lexicon Pharmaceuticals Protocol No. EFC14833

Date of Issue: 21-Nov-2019

Covance Study ID: 000000150524

EOSI	Preferred term code	Preferred term
Potentially leading to amputation	10061666	Autonomic neuropathy
Potentially leading to amputation	10061815	Diabetic vascular disorder
Potentially leading to amputation	10062198	Microangiopathy
Potentially leading to amputation	10062255	Soft tissue infection
Potentially leading to amputation	10062585	Peripheral arterial occlusive disease
Potentially leading to amputation	10062599	Arterial occlusive disease
Potentially leading to amputation	10062610	Ischaemic limb pain
Potentially leading to amputation	10062932	Wound treatment
Potentially leading to amputation	10064250	Staphylococcal osteomyelitis
Potentially leading to amputation	10064601	Iliac artery occlusion
Potentially leading to amputation	10065237	Osteomyelitis bacterial
Potentially leading to amputation	10065239	Osteomyelitis fungal
Potentially leading to amputation	10065240	Wound infection bacterial
Potentially leading to amputation	10065242	Wound infection fungal
Potentially leading to amputation	10068653	Bone abscess
Potentially leading to amputation	10069379	Peripheral arterial reocclusion
Potentially leading to amputation	10072170	Skin wound
Potentially leading to amputation	10072557	Peripheral artery restenosis
Potentially leading to amputation	10072560	Peripheral endarterectomy
Potentially leading to amputation	10072561	Peripheral artery bypass
Potentially leading to amputation	10072562	Peripheral artery stent insertion
Potentially leading to amputation	10072563	Peripheral artery stenosis
Potentially leading to amputation	10072564	Peripheral artery thrombosis
Potentially leading to amputation	10074396	Penetrating atherosclerotic ulcer
Potentially leading to amputation	10075118	Subperiosteal abscess
Potentially leading to amputation	10075714	Vasculitic ulcer
Potentially leading to amputation	10076246	Spontaneous amputation

Statistical Analysis Plan

Version: 3

Lexicon Pharmaceuticals Protocol No. EFC14833

Date of Issue: 21-Nov-2019

Covance Study ID: 000000150524

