### **10.3.1 Temporary treatment discontinuation with investigational medicinal product(s)**

Temporary treatment discontinuation may be considered by the Investigator because of suspected AEs. Lower extremity complications (such as skin ulcers, infection, osteomyelitis, and gangrene) requiring treatment should lead to temporary discontinuation of IMP. Reinitiating treatment with the IMP will be done under close and appropriate clinical and/or laboratory monitoring once the Investigator will have considered according to his/her best medical judgment that the occurrence of the concerned event was unlikely to be related to the IMP.

It is in the interest of the patient to monitor blood glucose during the temporary discontinuation period, therefore regular determination of SMBG is to be performed and documented.

For all temporary treatment discontinuations, duration should be recorded by the Investigator in the appropriate pages of the e-CRF when considered as confirmed.

Temporary treatment discontinuation decided by the Investigator corresponds to more than 1 dose not administered to the patient.

Use of any different anti-hyperglycemic medication during the time of temporary treatment discontinuation (ie, insulin during a hospitalization) is recorded as concomitant medication with the name and doses recorded in the e-CRF.

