Malignancies of special interest	Breast cancer: Narrow search on “Breast neoplasms, malignant and unspecified (SMQ)” [20000149] Prostate cancer: Narrow search on “Prostate neoplasms, malignant and unspecified (SMQ)” [20000152] Leydig-cell cancer: PTs of Leydig cell tumour of the testis (10024407) and Ovarian Sertoli-Leydig cell tumour (10073270) based on MedDRA v22.0 Thyroid cancer: PTs in Appendix C Renal cell cancer: PTs in Appendix C Pancreatic cancer: PTs in Appendix C Bladder cancer: PTs in Appendix C

EOSI AE leading to an amputation

Statistical Analysis Plan

Version: 3

Lexicon Pharmaceuticals Protocol No. EFC14833

Date of Issue: 21-Nov-2019

Covance Study ID: 000000150524

AE Grouping	Criteria
Adverse event leading to an amputation	"AE Correction" as the reason for amputation in eCRF "Other Procedures related to Amputation"
AE potentially leading to an amputation *	PTs in Appendix C

* Search terms will be updated using the MedDRA version currently in effect at Covance at the time of database lock for EOSI identified by them.

AE potentially leading to an amputation: not an EOSI per individual protocol; analyzed due to their relevance to lower limb complication and amputations as a requirement from health authorities.

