Bladder cancer	10005008	Bladder cancer stage I, with cancer in situ
Bladder cancer	10005009	Bladder cancer stage I, without cancer in situ
Bladder cancer	10005010	Bladder cancer stage II
Bladder cancer	10005011	Bladder cancer stage III
Bladder cancer	10005012	Bladder cancer stage IV
Bladder cancer	10005056	Bladder neoplasm
Bladder cancer	10005075	Bladder squamous cell carcinoma recurrent
Bladder cancer	10005076	Bladder squamous cell carcinoma stage 0
Bladder cancer	10005077	Bladder squamous cell carcinoma stage I
Bladder cancer	10005078	Bladder squamous cell carcinoma stage II
Bladder cancer	10005079	Bladder squamous cell carcinoma stage III
Bladder cancer	10005080	Bladder squamous cell carcinoma stage IV
Bladder cancer	10005081	Bladder squamous cell carcinoma stage unspecified
Bladder cancer	10005084	Bladder transitional cell carcinoma
Bladder cancer	10051690	Urinary bladder sarcoma
Bladder cancer	10057352	Metastatic carcinoma of the bladder
Bladder cancer	10066749	Bladder transitional cell carcinoma stage 0
Bladder cancer	10066750	Bladder transitional cell carcinoma recurrent
Bladder cancer	10066751	Bladder transitional cell carcinoma stage I
Bladder cancer	10066752	Bladder transitional cell carcinoma stage IV
Bladder cancer	10066753	Bladder transitional cell carcinoma stage II
Bladder cancer	10066754	Bladder transitional cell carcinoma stage III
Bladder cancer	10071664	Bladder transitional cell carcinoma metastatic
Bladder cancer	10078341	Neuroendocrine carcinoma of the bladder
Potentially leading to amputation	10003084	Areflexia
Potentially leading to amputation	10003178	Arterial thrombosis

Statistical Analysis Plan

Version: 3

Lexicon Pharmaceuticals Protocol No. EFC14833

Date of Issue: 21-Nov-2019

Covance Study ID: 000000150524

EOSI	Preferred term code	Preferred term
Potentially leading to amputation	10003210	Arteriosclerosis
Potentially leading to amputation	10003222	Arteriosclerotic gangrene
Potentially leading to amputation	10006784	Burning sensation
Potentially leading to amputation	10007904	Cellulitis enterococcal
Potentially leading to amputation	10007905	Cellulitis gangrenous
Potentially leading to amputation	10007921	Cellulitis staphylococcal
Potentially leading to amputation	10007922	Cellulitis streptococcal
Potentially leading to amputation	10012174	Dehydration
Potentially leading to amputation	10012665	Diabetic gangrene
Potentially leading to amputation	10012679	Diabetic neuropathic ulcer

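### The SAP's search list for adverse events potentially leading to amputation has four qualified cellulitis terms but not plain Cellulitis, so events coded to the plain term drop out of that descriptive table and listing (minor)

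*SAP*

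**What the plan says.** SAP section 2.1.4.2, Table 3, identifies an adverse event potentially leading to an amputation by one criterion, the preferred terms in Appendix C. The table's footnote explains why the category exists: "AE potentially leading to an amputation: not an EOSI per individual protocol; analyzed due to their relevance to lower limb complication and amputations". It adds that health authorities require the analysis.

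SAP section 2.4.5.2 (Analysis of Amputation) then plans the number and percentage of patients by treatment group and preferred term, with a listing that flags patients who had an amputation procedure. It says that the terms were requested in a European regulatory assessment report of 9 February 2017.

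The cellulitis rows in Appendix C are "Cellulitis enterococcal" (10007904), "Cellulitis gangrenous" (10007905), "Cellulitis staphylococcal" (10007921) and "Cellulitis streptococcal" (10007922).

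Protocol section 10.3.1 shows the clinical interest in this area: "Lower extremity complications (such as skin ulcers, infection, osteomyelitis, and gangrene) requiring treatment should lead to temporary discontinuation of IMP".

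**The concern.** The search works on preferred terms. An event whose coded term is plain cellulitis matches none of the four listed forms. The broader infection terms do not help either, because a match on *Skin infection* or "Soft tissue infection" does not pull in an event coded to a different term.

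Protocol section 10.4.2 asks investigators to report a diagnosis where possible, and the protocol plans urine culture but no skin culture. A report of cellulitis with no organism is therefore plausible.

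At stake is the completeness of one descriptive table and its listing. A difference between arms in plainly coded cellulitis would not show there, although the category was set up because of its relevance to lower-limb complications.

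**Working it through.** No figure in the plan bears on this point, so the check is a reading of the list.

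**1. Is the term really absent?** The rows labelled as potentially leading to amputation number 97, and their codes run in unbroken ascending order. The row before the cellulitis block is "Burning sensation" (10006784), and the row after it is *Dehydration* (10012174). Four rows contain the word cellulitis, and no row anywhere in the list reads plain *Cellulitis*. There is no gap or redaction mark, so loss of a row in text extraction is unlikely.

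**2. How does the list treat other families?**

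| Family | Related rows | Plain term listed? |
|---|---|---|
| Osteomyelitis | 7 | Yes (10031252) |
| Wound infection | 6 | Yes (10048038) |
| Gangrene | 4 | Yes (10017711) |
| Cellulitis | 4 | No |
| Abscess (subcutaneous, limb, wound, bone, subperiosteal) | 5 | No |
| Necrosis (ischaemic, wound, extremity) | 3 | No |

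The list also includes *Skin infection* (10040872), *Soft tissue infection* (10062255), *Localised infection* (10024774) and *Wound* (10052428). All four are less specific than plain cellulitis.

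**3. What exactly is lost?** Only events coded to the unqualified term are lost. "Cellulitis gangrenous" names no organism and is on the list, so gangrenous cellulitis is counted whether or not an organism is known.

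**4. Where do the lost events still appear?**
- The treatment-emergent adverse event tables by system organ class and preferred term, and the serious event tables where applicable (SAP 2.4.5.2).
- The supportive adverse event listings (SAP 2.4.5.2).
- If an amputation follows and correction of an adverse event is recorded as its reason, the separate count of adverse events leading to an amputation. That count uses the event identifier on the eCRF amputation page and does not depend on the preferred-term list.

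**5. Effect of the change.** The list goes from 97 to 97 + 1 = 98 terms, and the cellulitis terms from 4 to 4 + 1 = 5. The effect on patient counts cannot be computed. The documents give neither a cellulitis rate nor the share of cellulitis that would be coded to a qualified term.

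**The case against.** The strongest objection is the origin of the list. The SAP says that a regulator requested these terms, and the request is not available here. If plain cellulitis was not in it, Appendix C reproduces the request faithfully and an addition extends it. This stands, and it is why the first step of the fix is a check against the source. It does not fill the gap, because a footnoted addition leaves the requested count reproducible.

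A reader might infer from osteomyelitis, wound infection and gangrene that the omission must be a slip. The documents do not support that. Abscess and necrosis also lack their plain terms, so a missing parent term is not proof of error. What remains is that a list broad enough to count any wound or skin infection gives no visible reason to exclude plain cellulitis.

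A reader might also infer that lower-limb risk is assessed through this table alone. It is not. SAP 2.4.5.2 separately summarizes amputation procedures and the adverse events leading to them, both from the eCRF. Protocol section 6.4.3 sends amputation cases to an independent blinded committee.

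The footnote to Table 3 says that search terms will follow the MedDRA version in effect at database lock. That is a version update and does not promise to add a term that was never listed.

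**Conclusion.** The point holds as a minor gap. Followed as written, the plan leaves adverse events coded to unqualified cellulitis out of the table and listing of events potentially leading to amputation, while counting less specific infection and wound terms.

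The consequence is small. The category is descriptive and is not a protocol event of special interest. SAP 2.4.5 plans no systematic testing of safety variables, and the omitted events remain visible elsewhere. It is tempting to say that most cellulitis would be missed, or to put a percentage on it, but the documents give no basis for any such share. The number affected could be zero.

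The conclusion assumes that an unqualified *Cellulitis* preferred term exists in the MedDRA version used. The documents do not show the dictionary.

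**What to change.** Before database lock:

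1. Compare the amputation rows of Appendix C with the regulator's request, and confirm the unqualified term and its code in the MedDRA version in use.
2. Add *Cellulitis* to the list. If it was in the request, this restores it. If it was not, footnote it as an addition so that the count on the requested terms alone can still be produced.

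The cost is one row in Appendix C and one line in the search program. The downside is that some added events will not be in the lower limb. The broad skin and soft-tissue terms already listed have the same limitation.

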Appendix D Summary of statistical analyses

EFFICACY ANALYSIS

Endpoint	Analysis population	Primary analysis	Supportive analysis	Subgroup analysis	Other analyses
Primary endpoint					
HbA _{1c} : Change from baseline at Week 26, (sotagliflozin 400 mg vs placebo)	ITT	ANCOVA (with missing values imputed by the retrieved dropouts & washout imputation method or by control-based copy reference MI method under MNAR framework): treatment, randomization stratum (HbA _{1c} / SBP at screening), and country as fixed effects, and baseline HbA _{1c} value as a covariate, under the original protocol and Amendment 1	Tipping point analysis; ANCOVA (with missing values imputed by the retrieved dropouts & washout imputation method or by control-based copy reference MI method under MNAR framework) under original protocol and Amendment 1	Subgroups: race, ethnicity, age, gender, baseline BMI, baseline HbA _{1c} , baseline SBP, baseline eGFR and country.	Summary statistics for observed values and changes from baseline by visit. Graphical presentations for mean changes from baseline (\pm SE) and mean values (\pm SE) by visit. By-visit summary and graph excluding measurements after rescue therapy.
Secondary endpoints					
HbA _{1c} , 2-hour PPG, FPG, body weight: Change from Baseline to Week 26; SBP (for patients with baseline SBP \geq 130 mmHg, all patients): Change from Baseline to Week 12	ITT	ANCOVA (with missing values imputed by the retrieved dropouts & washout imputation method or by control-based copy reference MI Method under MNAR framework): treatment, randomization stratum (HbA _{1c} / SBP at screening), and country as fixed effects, and baseline HbA _{1c} value as a covariate, comparing sotagliflozin 400 mg vs placebo under the original protocol and Amendment 1, and comparing sotagliflozin 200 mg vs placebo	ANCOVA (with missing values imputed by the retrieved dropouts & washout imputation method or by control-based copy reference MI method under MNAR framework) comparing sotagliflozin 200 mg (for selected other endpoints) vs placebo under Amendment 1; Tipping point analysis on HbA _{1c} .	Subgroups on HbA _{1c} : race, ethnicity, age, gender, baseline BMI, baseline HbA _{1c} , baseline SBP, baseline eGFR and country.	Summary statistics for observed values and changes from baseline by visit. Graphical presentations for mean changes from baseline (\pm SE) and mean values (\pm SE) by visit.

Statistical Analysis Plan

Version: 3

Lexicon Pharmaceuticals Protocol No. EFC14833

Date of Issue: 21-Nov-2019

Covance Study ID: 000000150524

Endpoint	Analysis population	Primary analysis	Supportive analysis	Subgroup analysis	Other analyses
Proportion of patients with HbA _{1c} <6.5%, <7.0% at Week 26	ITT	under Amendment 1. CMH method stratified on randomization strata (HbA _{1c} / SBP at screening), comparing sotagliflozin 400 mg vs placebo under the original protocol and Amendment 1, and comparing sotagliflozin 200 mg vs placebo under Amendment 1.	CMH method stratified on randomization strata (HbA _{1c} / SBP at screening): excluding patients with baseline HbA _{1c} values <6.5% (for <6.5% responders) or <7% (for <7% responders) respectively	No	By-visit summary and graphs of HbA _{1c} responders (<6.5%, <7%). By-visit frequency summary and graphs of HbA _{1c} responders (<6.5%, <7%) excluding patients with baseline HbA _{1c} values <6.5% or <7% respectively.
Other endpoints					
SBP (for patients with baseline SBP <130 mmHg), DBP, Urine ACR, UGE, and urine GCR, Serum creatinine, eGFR: change from baseline	ITT	Summary statistics for observed values and changes from baseline by visit.	No	No	Graphical presentations for mean changes from baseline (\pm SE) and mean values (\pm SE) by visit as appropriate.
Proportion of patients, with reduction in body weight by $\geq 2\%$, $\geq 5\%$, and $\geq 10\%$ from Baseline; achieving SBP <130 mmHg with baseline SBP ≥ 130 mmHg; achieving DBP <80 mmHg with baseline DBP ≥ 80 mmHg	ITT	By-visit frequency summary	No	No	By-visit graphical presentation as appropriate
Proportion of patients requiring rescue for hyperglycemia		Summary statistics	No	No	KM plot; List of patients rescued

Statistical Analysis Plan

Version: 3

Lexicon Pharmaceuticals Protocol No. EFC14833

Date of Issue: 21-Nov-2019

Covance Study ID: 000000150524

SAFETY ANALYSES

Endpoint	Analysis Population	Primary analysis	Supportive Analysis	Subgroup analysis	Other analyses
hypoglycemia	Safety	Follow safety guidelines Number (%) of patients with any hypoglycemia, severe hypoglycemia, documented symptomatic hypoglycemia during TEAE period, and incidence rates in 100 patient-years.		Severe hypoglycemia or documented symptomatic hypoglycemia by subgroups: race, age, gender	KM plot time to first event of severe hypoglycemia or documented symptomatic hypoglycemia Documented symptomatic hypoglycemia maybe presented by <54 mg/dL (3.0 mmol/L) as appropriate.
Adverse Events	Safety	Follow safety guidelines	No	Common TEAEs by subgroups: race, age, gender, baseline SBP, baseline eGFR	
Clinical laboratory data	Safety	Follow safety guidelines	Descriptive	No	No
Vital signs	Safety	Follow safety guidelines	Descriptive	No	No
ECG, Physical examination	Safety	Follow safety guidelines	Frequency summary	No	No

Statistical Analysis Plan

Version: 3

Lexicon Pharmaceuticals Protocol No. EFC14833

Date of Issue: 21-Nov-2019

Covance Study ID: 000000150524

Appendix E Study flow chart

	Screening Period		Double Blind Treatment Period ^a								Follow-up ^b
	Screening	Run-in	3 (Randomization)	4	5	6	7	8	9	10	
VISIT	1	2	3 (Randomization)								
Week	Up to -4	-2	0 Baseline	1	4	8	12	18	26	30	
Day (window [days])		(-7/+3)	1	7 (±3)	28 (±3)	56 (±3)	84 (±3)	126 (±3)	182 (±3)	210 (±3)	
Informed consent	X										
Inclusion criteria	X										
Exclusion criteria	X		X								
Demographics	X										
Medical/Surgical History	X										
Medication History	X										
Body weight, height ^c	X	X	X	X	X	X	X	X	X	X	
Vital signs ^d	X	X	X	X	X	X	X	X	X	X	
Physical Exam:											
complete	X									X	
abbreviated		X	X	X	X	X	X	X		X	
Diet & exercise instruction		X	X							X	
Instruction on basic genitourinary hygiene & hydration		X	X	X	X	X	X	X	X	X	
Interactive response technology (IRT) contact	X	X	X		X	X	X	X	X	X	
Randomization			X								
Dispense glucose meter		X									
Dispense diary	X	X	X	X	X	X	X	X	X		
Collect/review diary		X	X	X	X	X	X	X	X	X	
Instruction on diabetic ketoacidosis symptoms and glucose testing			X	X	X	X	X	X	X		

Statistical Analysis Plan

Version: 3

Lexicon Pharmaceuticals Protocol No. EFC14833

Date of Issue: 21-Nov-2019

Covance Study ID: 000000150524

	Screening Period		Double Blind Treatment Period ^a								Follow-up ^b
	Screening	Run-in	3 (Randomization)	4	5	6	7	8	9	10	
VISIT	1	2	3 (Randomization)								
Week	Up to -4	-2	0 Baseline	1	4	8	12	18	26	30	
Day (window [days])		(-7/+3)	1	7 (±3)	28 (±3)	56 (±3)	84 (±3)	126 (±3)	182 (±3)	210 (±3)	
Dispense IMP		X	X		X	X	X	X			
IMP accounting & compliance			X	X	X	X	X	X	X		
Concomitant medication	X	X	X	X	X	X	X	X	X	X	
Self-monitored blood glucose ^e		X	X	X	X	X	X	X	X	X	
12-lead ECG ^f	X		X							X	
Standard mixed meal tolerance test ^g			X							X	
Laboratory testing^h											
FPG	X		X	X	X	X	X	X	X		
HbA1c	X		X		X	X	X	X	X		
Chemistry (including amylase and lipase)	X		X		X	X	X	X	X	X	
Hematology	X		X				X			X	
Fasting lipids	X		X		X	X	X	X	X	X	
Pregnancy test (WOCBP) ⁱ	X		X		X	X	X	X	X		
Serum follicle stimulating hormone and estradiol (menopausal women only) ^j	X										
Plasma concentration ^j					X			X	X		
Markers of intestinal transit & absorption ^k			X						X	X	
Markers of bone & calcium metabolism ^l			X						X		
Urinalysis (dipstick and microscopy) ^m	X		X						X		

Statistical Analysis Plan

Version: 3

Lexicon Pharmaceuticals Protocol No. EFC14833

Date of Issue: 21-Nov-2019

Covance Study ID: 000000150524

	Screening Period		Double Blind Treatment Period ^a								Follow-up ^b						
	Screening	Run-in	3 (Randomization)	4	5	6	7	8	9	10							
VISIT	1	2	3 (Randomization)	4	5	6	7	8	9	10							
Week	Up to -4	-2	0 Baseline	1	4	8	12	18	26	30							
Day (window [days])		(-7/+3)	1	7 (±3)	28 (±3)	56 (±3)	84 (±3)	126 (±3)	182 (±3)	210 (±3)							
Urine albumin, calcium, glucose & creatinine			X	X	X	X	X	X	X	X							
Evaluate for glycemic rescue					To be assessed and reported throughout the treatment period												
Hypoglycemia				To be assessed and reported throughout the study													
AEs/SAEs/AEIs/EOSIs				To be assessed and reported throughout the study ^p													

a If a patient discontinues treatment with IMP early during the Treatment Period, the patient will have a Premature EOT Visit, and a Follow-up Visit 4 weeks after the last dose of IMP. However, every effort will be made to have all patients return to the site for all scheduled visits, in particular the Week 26 Visit. If the patient does not agree to a site visit, they will be contacted by telephone to inquire about safety status. If a patient discontinues (or completes) treatment and study at the same time, a single visit will be performed using the procedure normally planned for the EOT visit.

b Four weeks after the last dose of IMP.

c Height to be measured only at screening

d Vital sign measurements (sitting BP and heart rate): 3 separate seated BP and heart rate measurements should be taken with at least 1 minute between readings, following a 5-minute rest period and prior to phlebotomy (see protocol Section 9.2.1.4 and detailed instructions in protocol Appendix D).

e See protocol Section 9.2.1.6 for details of SMBG measurements. Glucose meters used for SMBG display results as plasma glucose concentration. Patients should measure their fasting plasma glucose at least 3 times per week (including on day of each on-site study visit).

f The 12-lead ECG recordings should be obtained prior to IMP administration. The ECG will be evaluated as "normal" or "abnormal".

g Postprandial plasma glucose will be assessed by central laboratory at Baseline and 2 hours after consuming a standard mixed liquid breakfast meal and via a mixed meal tolerance test (MMTT) on Day 1 and Week 26. If a patient withdraws from IMP early, please see protocol Section 10.3.4.

h All laboratory assessments occur prior to first dose of double-blind IMP. The first dose of double-blind IMP occurs after samples for the mixed liquid meal have been collected. All visit dates will be scheduled based on the date of randomization with a ±3 days visit window allowed during the treatment period. Serum chemistry parameters (clinical chemistry [including amylase and lipase], hematology, and other blood parameters) are listed in protocol Table 2.

i Serum pregnancy testing only at screening; urine pregnancy testing subsequently. Serum pregnancy test results must be reviewed prior to beginning the Run-in Phase for all women of childbearing potential (WOCBP). Any positive urine test results must be confirmed based on serum pregnancy test. The Investigator may perform additional tests at their discretion or as required by local regulations. For women of nonreproductive potential (protocol Appendix A), follicle stimulating hormone (FSH) and/or estradiol levels should be tested if the definition of postmenopausal or premenopausal cannot be satisfied, eg, no medical document of hysterectomy or cessation of menses <12 months without an alternative medical cause.

Statistical Analysis Plan

Version: 3

Lexicon Pharmaceuticals Protocol No. EFC14833

Date of Issue: 21-Nov-2019

Covance Study ID: 000000150524

- j* Plasma concentration samples (ie, for sotagliflozin and sotagliflozin-3-O-glucuronide) on Weeks 4 and Week 18 should be drawn with the other laboratory assessments. For Week 26, plasma concentration samples should be drawn at predose and 2 hours 30 minutes, immediately after the respective glucose assessments during the MMTT. PK samples (except the 2 hours 30 minute sample during the MMTT) MUST be collected before administration of IMP. The date and time of the last intake of IMP prior to visits where PK samples are taken should be recorded by the patient in the patient diary. Patients should be reminded of this at visits preceding PK time points to ensure these details are captured. In the case of Premature IMP discontinuation, PK samples should not be drawn at the Premature EOT visit, nor at any subsequent visits.
- k* The markers of intestinal transit and absorption include vitamins B6, B12, K, E, and A, serum folate, and ferritin.
- l* Markers of bone and calcium metabolism include: serum and urinary calcium, serum 25-hydroxyvitamin D, serum 1,25-dihydroxyvitamin D, serum and urinary phosphorus, serum parathyroid hormone, markers of bone resorption (serum NTX, serum β -CTX-1), and bone formation (serum P1NP).
- m* Urinalysis includes urine dipstick and microscopy. Dipstick includes assessment of specific gravity, pH, protein, blood, ketones, bilirubin, urobilinogen, nitrite, and leukocyte esterase. Microscopy includes detection of formed cellular elements, casts, bacteria, yeast, parasites, and crystals in centrifuged urine sediment. In the event of abnormal urinalysis findings suspicious of urinary tract infection, urine culture should be performed. Positive urine culture determination will be based upon the criteria of the reporting laboratory.
- p* [REDACTED]
- p* All serious adverse events (SAEs), adverse events (AEs), AEs of special interest (AESIs), and Events of Special Interest (EOSIs) will be collected starting with signing informed consent and continue until the end of the study. All AEs that occur during treatment should be followed until study completion (or until patients leave the study) or until the event has resolved, the condition has stabilized, or the patient is lost to follow-up. All patients will have a follow-up contact 4 weeks after the last dose of IMP to collect safety information.
